Study staff delivering the intervention will participate in approximately eight hours of training initially with additional training as needed over the course of the study. The training, developed by [name], will include the purpose of the project and will review procedures and materials for use during the study. The PhD student will practice using materials and communicating with others during training. In addition, we will cover confidentiality, listening skills, strategies for coaching (but not directing) and sensitivity to cultural, ethnic, and related issues. During the intervention after obtaining the participants' permission, [name] will patch-in on a random sample of 5% of interactions to assure protocol fidelity and to provide comments to increase the effectiveness of the intervention.

Outcome measures

1. Anthropometric measures / Body composition

Body weight, height and waist circumference (WC) will be measured using procedures based on the most recent NHANES Anthropometry Procedures Manual [11] at the local health department or medical facility at the time of the screening blood draw, 3 month and 6 month blood draws. Briefly, participants will have their weight measured in light clothing without shoes on a regularly calibrated digital scale. Height will be measured using a well-mounted stadiometer. Waist circumference will be assessed in duplicate with a measured tape placed horizontally just above the iliac crest, after completion of a respiratory cycle. When available, we will also measure body composition (% body fat measured by bio-impedance scale). We will compare the initial measurements to the 3-month and 6-month weight measurements.

2. Blood measures

Blood samples will be collected at screening and repeated at 3 and 6 months.

Screening blood samples will be used to determine eligibility but will also be processed and stored for analysis of PBB, PCB, DDT/DDE, and PBDE concentrations with the participants' other study time points. Blood samples will be aliquoted into smaller vials and frozen at -70°C and stored for analysis at the completion of the study.

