Discontinuation from Orlistat does not mean discontinuation from the study, and remaining study procedures should be completed as indicated by the study protocol. If a clinically significant finding is identified (including, but not limited to changes from baseline) after enrollment, [name] will determine if any change in participant management is needed. Any new clinically relevant finding will be reported as an adverse event (AE).

The data to be collected at the time of study intervention discontinuation will include the following:

- Reason for discontinuing
- Participant will be asked to complete all study procedures including 3 month and 6 month blood draws for POPs determination.

The PI may discontinue or withdraw a participant from the study for the following reasons:

- Pregnancy

- Significant study intervention non-compliance
- If any clinical adverse event (AE), laboratory abnormality, or other medical condition or situation occurs such that continued participation in the study would not be in the best interest of the participant
- Disease progression which requires discontinuation of the study intervention
- If the participant meets an exclusion criterion (either newly developed or not previously recognized) that precludes further study participation
- Participant unable to receive Orlistat

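### Follow-up continues by default after stopping Orlistat, but three treatment-only reasons let the PI end study participation; where used, later ITT outcomes are lost

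*Combined protocol and SAP*

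**What the plan says.** All references are to the combined protocol and SAP.

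- **Default (Participant Discontinuation or Withdrawal).** "Discontinuation from Orlistat does not mean discontinuation from the study, and remaining study procedures should be completed as indicated by the study protocol". For those who stop the intervention: "Participant will be asked to complete all study procedures including 3 month and 6 month blood draws for POPs determination".
- **Exception (same section).** "The PI may discontinue or withdraw a participant from the study for the following reasons". Six reasons follow. Three concern treatment only: "Significant study intervention non-compliance", "Disease progression which requires discontinuation of the study intervention" and "Participant unable to receive Orlistat". The other three are pregnancy, an adverse event or similar situation subject to a best-interest test, and an exclusion criterion, worded as "If the participant meets an exclusion criterion (either newly developed or not previously recognized) that precludes further study participation".
- **Starting a listed medication (Participant Selection; Monitoring Procedures).** Participants who do so become ineligible during the study. Neither place says whether follow-up ends.
- **Pregnancy.** The Data Quality and Monitoring Plan stops the intervention. The withdrawal section lists pregnancy as a ground for leaving the study.
- **Outcome timing (Outcome measures, item 1).** Weight is taken "at the time of the screening blood draw, 3 month and 6 month blood draws".
- **Analysis (Statistical Modeling).** ITT, with a repeated-measures mixed model, a common baseline and continuous time. Random slopes may be added.

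**The concern.** The default and the exception can both be true, but nothing links them. A participant told to stop Orlistat for persistent gastrointestinal symptoms (AE Management) stays in follow-up under the default. The same person could also be read as unable to receive Orlistat and be withdrawn from the study. Significant non-compliance has no threshold, although the plan names its adherence measures.

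Weight is measured at the blood-draw visits, so leaving the study loses the primary outcome together with the POP levels. Values obtained before withdrawal stay in the mixed model, but the later ones are missing because of poor adherence or stopping treatment. The model then fills in those participants' course largely from people who stayed on treatment. That answers a question nearer to the effect in compliers than to ITT. Blinding of the PI does not remove this, because it occurs even when both arms lose the same share. The statistical section gives no sensitivity analysis for withdrawals, and an outcome never collected cannot be recovered in analysis.

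**Working it through.** The plan gives no figure for PI-initiated withdrawal, so there is none to reproduce. It counts such withdrawals within an anticipated total of about 20%. What follows is an illustration for weight.

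**Inputs from the plan.** SD of weight change 5 kg, 50 per arm, expected difference 2-3 kg (Power Analysis); 60 recruited per arm; the random-intercept model, with random slopes as an option (Statistical Modeling).

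**Assumptions not in the plan.** Orlistat effect in compliers 1.67 kg at month 3 and 2.5 kg at month 6 (2.5 is the midpoint of 2-3), and none in non-compliers. Programme loss 2 and 3 kg. Between-person SD 15 kg. SD of change 3.5 kg at month 3, correlated 0.8 with the month-6 change. All withdrawn participants would otherwise have attended.

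**Step 1: withdrawal before month 3, equal share w per arm.** Only the baseline remains for those withdrawn.

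- Full follow-up: ITT effect = (1 − w) × 2.5.
- With withdrawal, the model returns about 2.5.
- Overstatement = w/(1 − w), or w × 2.5 kg.
- w = 5% (3 of 60): 0.05/0.95 = 5.3%; 2.5 − 2.375 = 0.125 kg.
- w = 10% (6 of 60): 0.10/0.90 = 11.1%; 2.5 − 2.25 = 0.25 kg.

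**Step 2: withdrawal after month 3.** The month-3 weight already shows part of the lost effect, so the model corrects in part. A large-sample maximum-likelihood fit of the plan's model, compared with the same model under full follow-up, gives:

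| Withdrawn per arm | Random intercept | Random slope |
|---|---|---|
| 5% | 3.9% (0.09 kg) | 2.3% (0.05 kg) |
| 10% | 8.1% (0.18 kg) | 4.7% (0.10 kg) |

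**Step 3: sensitivity of the smallest figures.** With the correlation at 0.6, or the month-3 SD at 3 or 4 kg, the random-slope results run from 1.9% to 3.0% at 5% withdrawal and from 3.9% to 6.1% at 10%. The low ends are 0.019 × 2.375 = 0.05 kg and 0.039 × 2.25 = 0.09 kg. The overall ranges are therefore about 2-5% and 4-11%.

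**Step 4: milder assumptions.** If non-compliers get half the effect, the main-case ranges fall to 1.6-2.6% and 3.2-5.3%.

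**Step 5: scale.** Standard error of the difference = 5 × √(2/50) = 1.0 kg. Every shift above is at most a quarter of it.

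**Step 6: true null.** With no drug effect and equal withdrawal, both arms lose the same kind of participant and the shift is zero.

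PBB and the other POPs were not quantified.

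**The case against.** The strongest reply is that the protection is largely there already. The default keeps those who stop Orlistat in follow-up, AE Management follows the same pattern, every effort is made to regain contact after a missed draw, reasons are recorded, and the analysis is ITT. The PI's power is discretionary, and nothing shows that it would be used against the default. The phrase 'discontinue or withdraw' may partly mean stopping capsules. Pill counts are first reported at month 3, so for non-compliance the smaller, later-withdrawal figures are probably the relevant ones, although telephone calls also monitor adherence.

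Most of this stands, and it sets the severity. It does not close the gap: the text says withdrawal from the study, and no section continues outcome collection after it.

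A reader might infer more than the documents support:

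- *The power is unlimited.* It is not. The list is closed, and the adverse-event and exclusion-criterion items carry qualifiers. Disease progression also counts only where it forces the intervention to stop. What is missing is any link to outcome collection.
- *Data already collected are discarded.* No text says so.
- *The bias could be large.* A shift of 19.1% (0.40 kg) can be produced, but it needs 10% against 5% withdrawal under a blinded PI, all before month 3, no drug effect and complete loss of programme benefit in those withdrawn. With the imbalance reversed, results range from a 3.4% understatement to a 5.3% overstatement.

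**Conclusion.** The point holds as a gap in wording with a small expected effect. For three treatment-only reasons, the plan does not say whether its follow-up default or the PI's discretion governs. Where the discretion is used, weight and POP outcomes are lost in a way that works against the ITT commitment. The meaning of becoming ineligible, and of pregnancy, for follow-up is also unsettled.

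Under the stated assumptions the 6-month weight difference is overstated by about 2-5% (0.05-0.13 kg) at 5% withdrawal per arm, and by about 4-11% (0.09-0.25 kg) at 10%. The frequency is unknown, and the main inputs to these figures come from outside the plan. The documents do not support a claim that the clause would manufacture a drug effect: equal withdrawal rescales a real effect and leaves a true null at zero. Low severity, worth correcting because it is cheap and cannot be repaired afterwards.

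**What to change.** - In the withdrawal section, define stopping study capsules and leaving the study as two separate events.
- State that the three treatment-only reasons do not by themselves end outcome collection. These participants are still asked for the 3- and 6-month weights and blood draws, and the data stay in the ITT analysis, unless consent is withdrawn or another listed ground applies.
- Leave the best-interest, pregnancy and exclusion-criterion grounds as they are.
- Ask the sponsor to reconcile Participant Selection, the withdrawal section, Monitoring Procedures and the Data Quality and Monitoring Plan on whether becoming ineligible or pregnant ends the intervention only or follow-up as well. The answer is the sponsor's to give.
- Add the dates of both events to the existing CRF and report both by arm.

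The cost is protocol wording and two CRF dates; the visits are already scheduled. The downside is slightly more effort to retain non-adherent participants, some of whom will not attend. If only half do, about half of the bias is removed.

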PBB is a Persistent Organic Pollutant (POP). POPs are characterized by a very long half-life and storage in adipose (fat) tissue. Approximately 60% of 867 Registry participants recently tested still have elevated blood levels of PBB (above the 95%ile of NHANES, random sample of the US population) in their blood. PBB Research Registry participants have repeatedly asked whether weight loss could reduce their body burdens of PBB and if there was a way to speed elimination of PBBs. Orlistat is a reversible inhibitor of gastric and pancreatic lipases (enzymes that break down dietary fats for absorption in the intestines), thus inhibiting absorption of dietary fats by approximately 30% [1] and increasing excretion of fat into feces [2]. Orlistat was approved by FDA in 2007 as an over-the-counter aid to weight loss for overweight individuals. Although the weight loss attributed to Orlistat (compared to diet and exercise alone), is modest, the loss of body fat is much greater with Orlistat than diet and exercise alone.

We hypothesized that weight loss due to Orlistat, because it preferentially results in loss of adipose tissue, may also reduce blood levels of PBB and other POPs. There is biologic evidence that supports this hypothesis [3] and in a pilot study using a rodent model [4], Orlistat was shown to safely reduce body burden of lipophilic chemicals. In addition, the study suggested that the rate of toxicant elimination increases with a higher dose of Orlistat. A recent review of detoxification regimens noted the absence of randomized controlled trials and the need for such trials [5]. We proposed such a randomized controlled trial of Orlistat to provide some evidence of whether weight loss due to Orlistat may also reduce serum levels of POPs in a highly exposed community. The study was approved for funding by NIH/NIEHS.

OBJECTIVES

- The primary objective is to determine if the use of Orlistat results in weight loss that is accompanied by a reduction in the body burdens of PBB and other POPs.
- The primary endpoint is the change in weight and BMI in the Orlistat group compared to the placebo.
- The secondary endpoint is the change in serum concentrations of PBBs, PCBs, DDE, and PBDE in the Orlistat group compared to placebo.

STUDY DESIGN & METHODS

Study Overview

Title:

Use of a Weight Loss Aid in a population exposed to PBBs.

Study Description:

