Intervention: Orlistat is the active ingredient while the inactive ingredients include microcrystalline cellulose, povidone, sodium lauryl sulfate, and xylitol. Store at 20-25 °C (68-77°F.) FDA has approved a 60mg dose 3x daily with meals for over-the-counter sale. This is the lowest dose available of Orlistat. Higher doses require a prescription. The dosage will not change during the course of the trial (6 months for each participant). Upon enrollment we will dispense a three-month supply of Orlistat or placebo. At the end of month three they will receive a three-month supply.

Alli (trade name) or Orlistat is a weight loss aid for overweight adults, 18 years and older. It is recommended that Alli be accompanied by a reduced-calorie and low-fat diet and exercise program until weight loss goal is reached. Most weight loss occurs in the first 6 months, hence the 6-month duration of the trial. Participants will be instructed to take 1 capsule (60mg) with each meal containing fat, and not to take more than 3 capsules daily. These are the FDA-approved instructions provided in over-the-counter Alli. Orlistat may decrease absorption of fat soluble vitamins and thus a multivitamin will be provided for all participants to be taken once a day, at bedtime.

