The statistical hypothesis of interest is whether a mean change in weight or serum levels of POPs is detected at six months from the baseline. $H_0: \delta_I - \delta_P = 0$ vs $H_a: \delta_I - \delta_P > 0$, testing whether the mean change in weight or serum levels of POPs differs (mean change: δ , between the groups; δ_I , intervention group; δ_P , placebo group). The null hypothesis denotes no mean difference between the groups, and the one-sided alternative hypothesis denotes a difference between the groups, with the intervention group having a greater reduction in weight or serum levels of POPs over the course of the trial.

We plan to recruit and screen PBB registry participants, to enroll 120 participants into the trial. Our goal is to have 100 participants complete the 6-month trial duration. These estimates are based on the power analyses described here:

Power Analysis: The primary objective is to determine if the use of Orlistat results in weight loss in this population. Previous studies have shown an average of 2 to 3 kg weight difference between the intervention and placebo groups [16]. Assuming a standard deviation for weight change of 5 kg, we would have adequate power (80%) to detect a 2-3 kg difference ($\alpha=0.05$; $\rho=0.5$) in weight with a sample size of 50 in each group. Power analyses were performed in PASS 13 software [17].

The secondary endpoint is the change in serum concentrations of PBBs, PCBs, DDE, and PBDE at six months from the baseline. For the outcome of change in serum POP levels, we based our sample size estimations on the historical PBB data for PBB registry participants with at least 2 measurements within a year and the pilot data from Jandacek et al [18]. We estimate that the variance of the differences in PBB levels is expected to be between 0.1 and 0.2 log parts per billion (ppb) (σ^2_{diff}). We have used the pooled variances for our power calculations. From our historical data, we expect a 1% reduction in PBB levels due to the natural course of exposure. A sample size of 50 in each group, would provide at least 80% power to detect a mean change in log PBB levels of -0.1 and -0.2 log ppb with a significance level of $\alpha=0.05$.

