The health history questionnaire (already approved by IRB for the related study IRB# 45959) and an online version of the WHI-PAQ will be created using REDCap Software and available to participants through an online website. The Automated Self-Administered 24-Hour (ASA24) dietary assessment tool will be used to collect information on food consumption over the past 24 hours. Participants will complete the ASA24 at enrollment, 3 months and 6 months. If the participant prefers, the PhD student or authorized staff member will complete the assessments with the participant by telephone. Data from all questionnaires will be reviewed periodically for quality control, data entry errors, logical checks, and inconsistencies among related questions. Plausibility of outliers will be examined. All data related changes, including changes to the datasets will be documented electronically. Analytic datasets will be created to address specific study aims. Data dictionaries will be created. All data files will be maintained on a password-protected network system. Original and back-up datasets are stored on a secured network server.

Exploratory Analyses: Comparisons between the intervention and placebo groups will be conducted to assess the degree to which comparability of study groups was achieved. From the ASA24, we will calculate mean daily caloric, total fat, and carbohydrate intake. We will examine changes in these measures over the study period. From the WHI-PAQ, we will estimate physical activity intensity. Summary tables (descriptive statistics and/or frequency tables) will be provided for all baseline, follow-up, clinical, and exposure data. We will examine longitudinal trends through graphical methods, such as individual profile plots and plots of mean POP levels over time, by group. These plots will be inspected to characterize the within and between subject variations across time.

Statistical Modeling: Data will be analyzed according to the intention to treat (ITT) principle. We will use a repeated measures approach and mixed-effects models [19] where the dependent variable is either body weight in kg or natural-log PBB levels and the primary predictors of interest are the group variable (placebo or intervention) and the measurement time treated as a continuous variable.

The general random-intercept model notation is:

$$Y_{ij} = (\beta_0 + b_i) + (\beta_1 + \beta_2 X_i) t_{ij} + \varepsilon_{ij}$$

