where Y_{ij} denotes the weight in kg or the log-transformed serum PBB concentrations measured on participant i at time t_{ij} where $(i = 1, 2, \dots, n)$ for participants and $(j = 1, 2, \dots, n)$ for measurements within a participant. X_i is an indicator variable which takes the value zero for the placebo group and one for the intervention group. β_0 , represents the overall intercept (mean weight in kg or mean log PBB levels) at baseline, independent of group and b_i is the random effect that represents the deviation from the population mean for participant i . This model assumes that the random effect $b_i \sim N(0, \sigma_b^2)$ and the error $\varepsilon_{ij} \sim N(0, \sigma^2)$ are independent. β_1 and $(\beta_1 + \beta_2)$, represent the slopes (or elimination rates of PBB) for the placebo or the intervention group, respectively. The group-by-time interaction parameter $(\beta_2 X_i * t_{ij})$ assesses if the mean change in weight or if the PBB elimination rates vary by group across time. Slopes that vary randomly among participants will also be considered and an appropriate covariance structure will be selected.

Adjustment for relevant baseline variables and subgroup analyses will be performed to assess differences in weight change or PBB elimination rates by relevant covariates (such as age, gender, initial PBB level, or initial BMI). Since, physical activity reduces body weight and BMI, and increases metabolism, both may be associated with reducing PBB body burden. In multivariable models of serum PBB concentrations, we will consider adjusting for intensity of physical activity and change in BMI in order to measure the independent effect of Orlistat on reducing PBB levels. For the ASA24 measures, we will examine possible associations between changes in mean daily caloric, fat, and carbohydrate intake and serum PBB concentrations. Statistical analyses will be performed in SAS 9.4 software, and models will be fit with the Mixed procedure [19].

DATA & SAFETY MONITORING & REPORTING

Data Safety and Monitoring Plan

OVERSIGHT RESPONSIBILITIES

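### The stated 80% power for a 2-3 kg weight difference holds from about 2.5 kg upward, but at 2 kg it is 64% on change scores and at most 76% under the planned model at the stated rho of 0.5

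*Combined protocol and SAP*

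**What the plan says.** The Statistical Analysis section frames the question as "whether a mean change in weight or serum levels of POPs is detected at six months from the baseline" and specifies the direction: "the one-sided alternative hypothesis denotes a difference between the groups", with the greater reduction expected on Orlistat.

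Under Power Analysis, the expected effect on the primary endpoint is taken from earlier work: "Previous studies have shown an average of 2 to 3 kg weight difference between the intervention and placebo groups". The next sentence is the power claim: "Assuming a standard deviation for weight change of 5 kg, we would have adequate power (80%) to detect a 2-3 kg difference". It adds alpha 0.05, rho 0.5 and 50 per group. It names the software but not the procedure or test, and it does not say what rho correlates.

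Statistical Modeling then plans a random-intercept model with "the measurement time treated as a continuous variable". Its intercept is defined as "mean weight in kg or mean log PBB levels) at baseline, independent of group", so the arms share one baseline mean and the treatment effect is the difference in slopes. Weight is measured at screening, 3 months and 6 months.

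On numbers, Power Analysis sets at least 60 per group to allow for 20% attrition, citing 18% in an earlier trial. Participant Selection describes enrolment as 20% above the final target. Participant Discontinuation or Withdrawal allows treated participants who leave to be replaced only if withdrawals exceed roughly 20%.

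**The concern.** The plan gives 2 to 3 kg as the expected effect and straight away attaches a single power of 80% to the same range. One power figure cannot apply to a range of effects. The natural reading is that power is at least 80% throughout, and then the claim has to hold at 2 kg.

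The low end cannot be set aside. The Introduction says that "the weight loss attributed to Orlistat (compared to diet and exercise alone), is modest". The Intervention paragraph says of the trial's dose: "This is the lowest dose available of Orlistat". The documents do not say which dose produced the 2 to 3 kg.

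This is the power statement for the primary endpoint. A reader who takes 80% at face value would put the risk of missing a true 2 kg benefit at 20%. If the real risk is well above that, a null result would be over-interpreted.

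**Working it through.** **Inputs, all from Power Analysis and the hypothesis paragraph:** SD of weight change 5 kg; 50 per arm; alpha 0.05, one-sided; effect 2 to 3 kg; outcome is change at six months; rho 0.5, undefined.

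**1. Six-month change scores.** SE = 5 × √(2/50) = 1.000 kg. One-sided power = Φ(δ/SE − 1.645):

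- 2 kg: Φ(0.355) = 63.9%
- 2.5 kg: Φ(0.855) = 80.4%
- 3 kg: Φ(1.355) = 91.2%

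The noncentral t gives 63.4%, 79.9% and 90.9%. The plan's 80% is therefore reproduced at 2.5 kg and not at 2 kg. The difference with 80% power is (1.645 + 0.842) × 1.000 = 2.49 kg.

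Sample size per arm for 80% power is 2 × 25 × (2.486)²/δ². That is 49.5, rounded up to 50, for 2.5 kg, and 77.3, rounded up to 78, for 2 kg. With 50 per arm, 80% at 2 kg would need an SD of change of 2/(2.486 × 0.2) = 4.02 kg.

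**2. The planned mixed model.** Scale time so that six months is 1 and the visits are at 0, 0.5 and 1. A random intercept implies equal correlation rho between visits. Holding the SD of change at 5 kg fixes the residual variance at 25/2 = 12.5 and the SD of weight at each visit at 5/√(2(1 − rho)). With a common intercept, generalised least squares gives, for the six-month difference between arms,

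SE = √(2/(n·c)), where c = [1.25 − 2.25·rho/(1 + 2·rho)]/12.5.

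- rho 0.5: c = (1.25 − 0.5625)/12.5 = 0.0550, SE = 0.853
- rho 0.9: c = (1.25 − 0.7232)/12.5 = 0.0421, SE = 0.974
- rho 0.97: c = (1.25 − 0.7423)/12.5 = 0.0406, SE = 0.992

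If each arm has its own intercept, SE returns to 1.000 at any rho. The whole gain comes from the shared baseline.

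**3. Results, 50 per arm, one-sided 0.05**

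| Analysis | Implied SD of weight per visit | 2 kg | 2.5 kg | 3 kg | 80% point |
|---|---|---|---|---|---|
| Change scores | not needed | 63.9% | 80.4% | 91.2% | 2.49 kg |
| Planned model, rho 0.5 | 5.0 kg | 75.8% | 90.1% | 96.9% | 2.12 kg |
| Planned model, rho 0.9 | 11.2 kg | 65.8% | 82.2% | 92.4% | 2.42 kg |
| Planned model, rho 0.97 | 20.4 kg | 64.4% | 80.9% | 91.6% | 2.47 kg |

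The rho values of 0.9 and above are assumed. They correspond to body-weight SDs of about 11 to 20 kg, and the documents give no such SD.

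A two-sided test would be weaker: 51.6%, 70.5% and 85.1% on change scores (80% point 2.80 kg), and 65.0%, 83.4% and 94.0% in the model at rho 0.5 (80% point 2.39 kg).

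**4. Attrition.** 60 × 0.80 = 48, and 60 × 0.82 = 49.2. The 60 comes from 50 × 1.20. To keep 50 after a 20% loss takes 50/0.80 = 62.5, so 63. The aim of 50 completers is missed once loss passes 1 − 50/60 = 16.7%. With 48 per arm, one-sided power at 2 kg is 62.4% (change scores), 74.3% (model, rho 0.5) or 64-63% (model, rho 0.9-0.97), about 1.5 points below the figures for 50.

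**The case against.** **The sentence has a correct reading.** It may mean that the difference detectable with 80% power lies within 2 to 3 kg, and every 80% point in the table does. This stands as a possible reading. It still hides where in the range the threshold falls and gives false comfort at 2 kg.

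**A change-score test is probably not what was run.** Such a test uses no rho, and the plan calls for a mixed model. At the only rho in the documents that model gives 76% at 2 kg, about 4 points short. This is fair, and the software run cannot be recovered. But rho 0.5 as a between-visit correlation implies that body weight varies between participants with an SD of only 5 kg. A still lower correlation would do better (82% at rho 0.3), but it implies a visit SD of 4.2 kg and is not the value stated.

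**Other repeated-measures calculations come close to 80% at 2 kg.** With 5 kg as the SD of a single weight and rho 0.5, a three-visit average gives 78.9% under equal correlation and 82.0% under AR(1), one-sided. ANCOVA on the mean of the two follow-up weights gives 88.2% one-sided and 80.7% two-sided. One of these may be where the figure came from. They do not support it, because the plan says 5 kg is the SD of weight change, and these methods test a level averaged over visits, not the six-month change or the planned slope difference.

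**The dose argument is only suggestive.** No section gives a dose-response for weight, so the lowest dose does not show that 2 kg is the likely effect. It shows only that 2 kg cannot be dismissed.

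**The attrition cost is smaller in practice.** Analysis is by intention to treat with a mixed model, so partial data count. If half of the 12 dropouts per arm supply a month-3 weight (an assumption), power at 2 kg is 75.4% at rho 0.5 and 65.5% at rho 0.9, against 75.8% and 65.8% with 50 completers. Most of the 1.5 points is recovered.

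**The plan already admits uncertainty about sample size.** It attributes this to the variance estimates. The shortfall here arises at the stated SD.

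**Conclusion.** The concern holds. On the plan's own inputs, 80% power is available from about 2.5 kg upward and not at 2 kg. At a true 2 kg difference the one-sided risk of missing the benefit is about 36% on change scores, 24% under the planned model if rho 0.5 is the between-visit correlation, and 34-36% under that model at correlations of 0.9 or more. The implied risk is 20%.

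The change-score result needs nothing beyond the stated SD, sample size, alpha and one-sided alternative. The high-correlation result rests on an assumed spread of body weight. The favourable result rests on reading the undefined rho as the between-visit correlation.

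This is a misstated power figure for the primary endpoint and should be corrected, but it does not undermine the design. The attrition slip is correct and minor.

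**What to change.** Restate the power sentence so that it names the test, the one-sided alpha and the role of rho, with the change-score figures first because they do not depend on rho. For example:

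> With an SD of six-month weight change of 5 kg, one-sided alpha 0.05 and 48-50 evaluable participants per arm, a two-sample comparison of change has power of about 62-64% for a difference of 2 kg, 79-80% for 2.5 kg and 90-91% for 3 kg. The planned mixed model raises this to about 74-76%, 89-90% and 96-97% if the between-visit correlation is as low as 0.5. If that correlation is 0.9 or more (assumed; no SD of body weight is available), power for 2 kg is about 63-66%.

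A shorter alternative is to replace the 2-3 kg range by 2.5 kg, with one-sided alpha 0.05, change scores and 50 per arm stated.

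For attrition, say that 60 per group is 20% above the target of 50, and that 20% attrition leaves 48 (18% leaves 49). Reconcile this with the replacement threshold of about 20% in Participant Discontinuation or Withdrawal, since the aim of 50 completers is already missed once loss passes 16.7%.

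The cost is protocol wording and a less favourable stated power at 2 kg. No participants are added, and the design, endpoint and analysis do not change.
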